8.10 Stopping rules

The trial may be stopped before completion on the recommendation of the sponsor and CI and following guidance from the DMC following an interim analysis or at any stage during the study.

8.11 Definition of end of trial

Recruitment rate is estimated to range from 3 to 6 participants per week. Recruitment is estimated to take 12-15 weeks.

The expected duration of the trial is 3 – 4 months from recruitment of the first participant to last follow-up visit.

The end of trial is the date of the last visit of the last participant.

9 Recording and reporting of adverse events and reactions

Collection, recording and reporting of adverse events (including serious and non-serious events and reactions) to the sponsor will be completed according to the sponsor's SOP (INV/S05).

9.1 Definitions

Term	Definition	
Adverse Event (AE)	Any untoward medical occurrence in a participant administered dornase alfa and which does not necessarily have a causal relationship with this treatment. Therefore, an AE can be any unfavourable or unintended change in the structure (signs), function (symptoms) or chemistry (laboratory data) in a participant to whom dornase alfa has been administered, including occurrences which are not necessarily caused by or related to that product.	
Adverse Reaction (AR)	Any untoward and unintended response in a participant to dornase alfa which is related to any dose administered to that participant. This includes medication errors, uses outside of protocol (including misuse and abuse of product)	
Serious Adverse Event (SAE), Serious Adverse Reaction (SAR) or Unexpected Serious Adverse Reaction	 misuse and abuse of product) Any adverse event, adverse reaction or unexpected adverse reaction, respectively, that: results in death, is life-threatening*, requires prolongation of existing hospitalisation**, results in persistent or significant disability or incapacity, or consists of a congenital anomaly or birth defect 	

	* A life-threatening event, this refers to an event in which the participant was at risk of death at the time of the event; it does not refer to an event which hypothetically might have caused death if it were more severe.
	** Hospitalisation is defined as an in-patient admission, regardless of length of stay. Hospitalisation for pre-existing conditions, including elective procedures do not constitute an SAE.
	Some medical events may jeopardise the subject or may require an intervention to prevent one of the above characteristics/consequences. Such important medical events should also be considered as serious.
	The term " severe " is often used to describe the intensity of an event or reaction (e.g. mild, moderate or severe) and should not be confused or interchanged with the term " serious ".
Suspected Unexpected Serious Adverse Reaction (SUSAR)	A serious adverse reaction, the nature, severity or outcome of which is not consistent with the Reference Safety Information.
Reference Safety Information (RSI)	A list of medical events that defines which reactions are expected for the IMP being administered to clinical trial subjects, and so do not require expedited reporting to the Competent Authority. It is contained in a specific section in the Summary of product characteristics (SmPC) or the Investigator Brochure (IB).

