9.3.4 Seriousness

All events are assessed for seriousness as defined for an SAE in section 9.1.

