9.4 Procedures for recording and reporting Serious Adverse Events

All serious adverse events (SAEs/SARs/SUSARs) will be recorded in the medical records in the first instance. Serious Adverse Events (SAEs) related to COVID-19 will not be collected in the CRFs or reported to Sponsor for this trial.

All other SAEs will be recorded in the CRF, and the sponsor's SAE Recording Log and SAE Reporting Form.

All SAEs will be recorded from randomisation until 24h after last study dose.

All SAEs (except Covid-19 related SAEs specified in section as not requiring reporting to the Sponsor), must be recorded on a serious adverse event (SAE) Reporting Form. The CI/PI or designated individual will complete the sponsor's SAE form and email to the Sponsor at [contact], within 24 h of his/her becoming aware of the event. The Chief or Principal Investigator or designee will respond to any SAE queries raised by the sponsor as soon as possible.

Completed SAE forms must be sent within 24 hours of becoming aware of the event to the Sponsor Email forms to [contact]

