#### 11.4 Safety analyses

Safety of dornase alfa will be assessed by comparisons of adverse events (AEs), serious adverse events (SAEs), treatment-emergent adverse events (TEAEs) and deaths. The safety population is defined in Section 6.4.

All AEs will be summarized by BAC + dornase alfa/BAC only. A TEAE is an AE that starts or worsens at any time after initiation of study drug on Day1 through to end of follow-up.

For SAEs occurring in  $\geq$ 5% of individuals, follow-up-adjusted event rates based on events by randomised arm will be provided. The rates will be calculated as the total number of events in the randomised arm divided by the total sum of days follow-up in that randomisation arm, multiplied by 365.25, to give the expected number of events per patient year.

Listings of all TEAEs and SAEs will be provided.

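### The SAE definition in Protocol 9.1 has no criterion for a new in-patient admission, which does not fit its own footnote and leaves a suspected reaction that causes readmission to rest on other seriousness criteria

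*Protocol*

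**What the plan says.** Protocol 9.1 lists five outcomes that make an event serious: death, threat to life, an event that "requires prolongation of existing hospitalisation", lasting disability, and congenital anomaly. A general clause adds events that may jeopardise the participant or need intervention to avert one of these outcomes: "Such important medical events should also be considered as serious".

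The third item carries a double-asterisk footnote, which reads: "Hospitalisation is defined as an in-patient admission, regardless of length of stay". It continues: "Hospitalisation for pre-existing conditions, including elective procedures do not constitute an SAE".

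Other sections depend on this list. Protocol 9.3.4 states: "All events are assessed for seriousness as defined for an SAE in section 9.1". Section 9.1 defines a SUSAR as "A serious adverse reaction, the nature, severity or outcome of which is not consistent with the Reference Safety Information". Protocol 9.4 sets the recording period: "All SAEs will be recorded from randomisation until 24h after last study dose". SAP 11.4 compares adverse events and SAEs between the arms without a definition of SAE of its own, and counts treatment-emergent events that start or worsen "at any time after initiation of study drug on Day1 through to end of follow-up".

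**The concern.** An SAE definition would be expected to cover both an event that causes admission and one that lengthens a stay. Here only the second is present. Participants start the trial as in-patients, which may explain the omission, but that is an inference; the documents do not say so. Protocol 9.8 treats participants as in hospital throughout the trial, whereas Protocol 8.4.1 and Appendix 1 provide for discharge before Day35, so a new admission is possible.

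At stake is consistent classification of a suspected drug reaction in a population new to the drug. Protocol 3.1 describes this as the first use in COVID-19 and allows that safety may differ from that seen in cystic fibrosis. If two assessors read the list and the footnote differently, one could send a readmission down the SAE and SUSAR route and the other could leave it as a non-serious event.

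**Working it through.** No figure in the plan bears on this point and no arithmetic applies. The check is a comparison of the relevant sections.

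1. **List against footnote (Protocol 9.1).** The list admits only a lengthened stay. The footnote defines hospitalisation as any admission and exempts those for pre-existing conditions or elective procedures. An exemption for some admissions has a purpose only if other admissions count, and under the list none does. This is a mismatch by implication.

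2. **What depends on the list.** Section 9.3.4 refers all seriousness assessments to 9.1. The 24-hour report to the sponsor (9.4), the SUSAR notifications (9.6) and the SAE rates and listings (SAP 11.4) all presuppose that classification.

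3. **Whether a new admission can occur.** Protocol 8.4.1 plans a Day35 telephone call to those already discharged. Appendix 1 puts the final visit at discharge or Day35, whichever is first. SAP 10.1 also foresees discharge before seven days of follow-up are complete.

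4. **Where the wording changes the outcome.**
   - *SUSARs.* Protocol 9.6 requires notification of all SUSARs. Its 7-day and 15-day limits run from when the sponsor learns of the event; it sets no limit on how long after dosing the reaction may occur. A late suspected reaction leading to admission is therefore within scope only if it is serious on another criterion.
   - *Within 24 hours of the last dose.* Such an admission falls inside the 9.4 window. It would require discharge and return within a short interval.
   - *BAC-only arm.* These participants receive no dornase alfa, so the end of the 9.4 window is undefined for them, although SAP 11.4 compares the arms. The adverse event definition in 9.1 is itself worded for participants given dornase alfa, which makes the rule for this arm less clear still.

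5. **Where it does not.** Other post-discharge admissions lie outside the 9.4 window. SAP section 4 ends follow-up at the earliest of discharge, death or 35 days. The Day35 call is described as asking about breathing, with no stated question on readmission. COVID-19-related SAEs are kept out of the CRF and sponsor reporting by 9.2, 9.4 and 9.5.

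**The case against.** The strongest reply is that the definition is not what limits capture. Dosing is given by hospital staff (Protocol 9.9) and SAE recording stops 24 hours after the last dose, so most readmissions would go unrecorded under any definition. This stands, and it confines the point to the three situations above. It could be argued that the 9.4 window limits SUSARs too, but 9.6 does not say so.

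A second reply is that the important-medical-event clause and the life-threatening item already cover the admissions that matter. They would cover some. The clause does, however, call for a judgement on each event, in an open-label trial, whereas the fact of admission can be checked in the record. The contrast should not be pressed too far, since deciding that an event requires a longer stay is also a judgement.

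A third is that Protocol section 9 places collection and reporting under a sponsor SOP that may contain the missing criterion. That cannot be checked from the documents, and 9.3.4 points to 9.1, not to the SOP.

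A reader might also go further and say that the list contradicts its footnote outright. It does not. The footnote defines a term and exempts certain admissions; it never states that the remaining admissions are serious.

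**Conclusion.** The wording defect is real and should be corrected. A suspected unexpected reaction that leads to readmission has no hospitalisation criterion to meet, and its SUSAR status would turn on the other seriousness criteria. The effect is confined mainly to SUSARs, to admissions within 24 hours of the last dose, and to the BAC-only arm.

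Two stronger conclusions are tempting, and the documents support neither.

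- A reader might infer that SAP 11.4 would tabulate a readmission as non-serious. On the current text, follow-up ends at discharge, so a later admission would probably not be tabulated at all.
- A reader might estimate the SAEs lost by applying assumed discharge and readmission rates to all 40 participants. The documents give no such rates. The result would be an all-cause count that includes the 10 participants planned for BAC alone, COVID-19-related events excluded from reporting anyway, admissions outside the recording window, and events serious on other grounds.

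No defensible number can be given. That few reports are affected is a judgement from the narrow window and the exclusions.

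**What to change.** In the third item of the seriousness list in Protocol 9.1, insert *hospitalisation or* after *requires*, and keep the footnote and its marker. State in SAP 11.4 that SAE counts use this definition, and align the SAE form guidance.

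In the same amendment, reconcile 9.1 with Protocol 8.4.1 (Day35 call), 9.4 (recording window), 9.8 (participants assumed to be in hospital throughout), Appendix 1 (final visit at discharge) and SAP section 4 (end of follow-up). State when SAE recording ends in the BAC-only arm. Without this, the new wording alone would capture few readmissions.

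The definition itself costs two added words and an update to the form guidance. The downside is possibly a few more SAE reports.

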9.2 Recording adverse events

All adverse events will be assessed every day and recorded in the medical records in the first instance.

All adverse events will be recorded with clinical symptoms and accompanied with a simple, brief description of the event, including dates as appropriate.

Non-serious Adverse Events (AEs) and Serious Adverse Events (SAEs) related to COVID-19 will not be collected in the CRFs or reported to Sponsor for this trial.

The following events listed below describe anticipated Covid-19 related AEs:

Worsening respiratory failure, fever, venous thrombo-embolic disease, worsening respiratory failure, hospital-acquired secondary infection, organ-failure, lymphopenia, rising CRP, death.

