6.1 Recombinant Human DNase (dornase alfa)

Genentech (a wholly owned subsidiary of Roche) and Chugai Pharmaceutical developed and launched an inhalation solution (Pulmozyme) of dornase alfa, a highly purified recombinant human deoxyribonuclease (dornase alfa), for daily administration in conjunction with standard therapies. The product is indicated for the management of people with cystic fibrosis (CF) to improve pulmonary function. Dornase alfa is safe and well tolerated in adults and children.

Dornase alfa was launched in the US for the management of mild-to-moderate CF in conjunction with standard therapies in January 1994; in December 1996, the FDA expanded approval for use in CF participants with advanced CF. In April 1994, the drug was launched in the UK and Ireland, and by October 1994, it had been launched in France and Germany. In June 2012, dornase alfa was launched in Japan for the improvement of pulmonary function in participants with CF.

In December 2014, the FDA approved the eRapid Nebuliser System from PARI to deliver dornase alfa and to reduce treatment times (three minutes to deliver 2.5mg).

The recommended dosage is one 2.5 mg single-use ampule inhaled once daily using a recommended nebuliser jet nebuliser/compressor system or eRapid[™] Nebuliser System. Some participants (older/refractory) benefit from twice daily administration. (FDA label and EMA SmPC).

The most common adverse reactions (occurring in \ge 3% of participants treated with dornase alfa over placebo) seen in clinical trials in CF participants were: voice alteration, pharyngitis, rash, laryngitis, chest pain, conjunctivitis, rhinitis, decrease in FVC of \ge 10%, fever, and dyspnoea.

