9.5 Serious Adverse Events which do not require immediate reporting

The following events listed below describe anticipated COVID-19 related AEs:

Worsening respiratory failure, fever, venous thrombo-embolic disease, worsening respiratory failure, hospital-acquired secondary infection, organ-failure, lymphopenia, rising CRP, death.

These SAEs will be RECORDED in the participants' medical notes. They will not be recorded in the CRF or SAE Recording Log and SAE Reporting Forms will not be completed and sent to the sponsor.

If the frequency or severity of these events is not consistent with the COVID-19, the event must be reported to the sponsor as an SAE in the normal way.

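### Events attributed to COVID-19 stay out of the CRF, so the planned AE and SAE comparison by arm is selective and can mask fever, dyspnoea and thrombo-embolism

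*Protocol*

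**What the plan says.** Protocol 9.2 puts non-serious events and SAEs under one rule: "Serious Adverse Events (SAEs) related to COVID-19 will not be collected in the CRFs or reported to Sponsor for this trial". Its list of anticipated COVID-19 events has eight distinct terms, one of them printed twice. They are worsening respiratory failure, fever, venous thrombo-embolism and then "hospital-acquired secondary infection, organ-failure, lymphopenia, rising CRP, death".

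Protocol 9.4 repeats the rule for SAEs. Protocol 9.5 leaves these events in the medical notes and adds: "They will not be recorded in the CRF or SAE Recording Log and SAE Reporting Forms will not be completed and sent to the sponsor". It makes one exception. "If the frequency or severity of these events is not consistent with the COVID-19", the event is reported as an ordinary SAE.

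Protocol 9.1 defines an AE as "Any untoward medical occurrence in a participant administered dornase alfa". SAP 6.4 puts both randomised arms in the safety population. SAP 11.4 says: "Safety of dornase alfa will be assessed by comparisons of adverse events (AEs), serious adverse events (SAEs), treatment-emergent adverse events (TEAEs) and deaths". The interim analysis in Protocol 11.4 includes a description of AEs by treatment.

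Protocol 6.1 lists ten common adverse reactions to dornase alfa, ending with "fever, and dyspnoea".

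**The concern.** The safety tables are to be built from AE and SAE records that leave out whatever the investigator puts down to the disease. The trial is open-label, so that judgement is made with the arm known, and the amount left out can differ between arms. Some of the excluded events are ones that the drug might itself cause or worsen.

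Protocol 3.1 describes a first use of the drug in COVID-19, with sentinel dosing and a Type B risk class, and it names the DMC as the mitigation for the listed reactions. If the DMC's AE data carry the same exclusion, a clean table could reflect the recording rule as much as the drug. Nothing in SAP 11.4 would warn a reader of this.

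**Working it through.** The plan gives no figure on this point, so there is none to reproduce. The check sets the lists side by side and then asks how much the comparison could show.

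**1. Known reactions against the exclusion list.** Protocol 6.1 lists voice alteration, pharyngitis, rash, laryngitis, chest pain, conjunctivitis, rhinitis, FVC decrease, fever and dyspnoea.
- Excluded by name: 1 of 10 (fever).
- Plausibly recorded under an excluded label: 1 of 10 (dyspnoea, as worsening respiratory failure).
- Not on the list: 8 of 10.

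**2. The eight excluded events, and where else they appear.**

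| Event | Other source | Analysed in the SAP? |
|---|---|---|
| Worsening respiratory failure | Oxygen data (Protocol 8.4.1), WHO score, ventilation, ICU stay, respiratory rate | Partly |
| Fever | Temperature over 7 days | Descriptive only |
| Venous thrombo-embolism | None (D-dimer is a laboratory marker) | No |
| Hospital-acquired infection | Pneumonia | Partly |
| Organ failure | SOFA (Protocol 8.4.1) | No |
| Lymphopenia | Lymphocyte count | Yes |
| Rising CRP | Primary endpoint | Yes |
| Death | EPIC mortality (SAP 2.2.2) | Yes, survival (SAP 11.2) |

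Time on oxygen adds 24 hours for any oxygen on a day, whatever the amount (SAP 11.2), so it does not show escalation. The secondary analyses use the primary analysis population, which adds matched historical controls to the BAC arm. Only the WHO score is restricted to randomised patients.

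**3. What selective recording can do.** If the true rate in an arm is p and a share a of the events is attributed to COVID-19, the recorded rate is p × (1 − a). The recorded difference then depends on a in each arm as well as on the drug. The documents give no fever rate, so assume 30% on BAC and 60% on dornase alfa. Expected fevers are 0.30 × 10 = 3 and 0.60 × 30 = 18. With a = 1 in both arms, the AE table shows none.

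**4. Rules for attribution.** Protocol 9.3.2 calls an event drug-related unless that can be ruled out. Protocol 9.2 drops it if it is COVID-19 related. No rule covers an event that could be both. Protocol 9.3 asks for causality on every AE, and 9.3.2 captures it in the CRF/AE log or SAE form, but 9.2 and 9.5 keep the excluded events off the CRF and the SAE form. The heading of 9.5 speaks of immediate reporting only, while its text removes the events from the CRF.

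**5. The comparator arm.** The AE definition (Protocol 9.1) and the TEAE definition (SAP 11.4) both start from study-drug administration, which BAC patients never have.

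**6. What full collection would gain.** Two-sided Fisher exact test at 5%, 30 against 10, with fever on BAC assumed at 30%. Power is the sum, over tables with p < 0.05, of Bin(x; 30, p1) × Bin(y; 10, 0.30).

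| Fever rate on dornase alfa (p1) | Power |
|---|---|
| 33% | 3% |
| 40% | 5% |
| 50% | 12% |
| 60% | 27% |

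For a reaction that is not excluded, the chance of at least one case among 30 treated is 1 − (1 − p)^30. This gives 60% at p = 3%, 79% at 5% and 96% at 10%.

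**The case against.** The strongest reply is that most of the excluded events are measured in another way, as the table shows, and that the trial has other safeguards. The site is single, AEs are assessed daily, the first three participants are dosed one at a time, and the DMC meets weekly. The exception in Protocol 9.5 covers severity as well as frequency, and severity can be judged case by case. SAEs are recorded from randomisation and the AE review is not restricted by arm, so the AE definition may be a matter of wording. Finally, power is low even with full collection.

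Much of this stands, and it rules out several stronger readings:

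- A reader might infer that the SAP comparison cannot detect the drug's known reactions. Eight of the ten are not on the exclusion list. An FVC fall could be missed because spirometry is not scheduled, but this rule is not the cause. Death and thrombo-embolism are not among the listed reactions.
- A reader might infer that deaths are lost. At the 4–15% mortality in Protocol section 3, 0.04 × 40 = 1.6 to 0.15 × 40 = 6 deaths would be expected. They could be absent from SAE listings and rates, but EPIC mortality and the survival analysis still count them.
- A reader might infer that the 9.5 exception cannot work. It can for severity. It has no threshold, though, and frequency is hard to judge by arm when the events are not tabulated.
- The sentence in 9.2 could be read as excluding all non-serious AEs. Protocol 9.3.2 (causality in the CRF or AE log) and SAP 11.4 (all AEs summarised) point to the narrower reading.

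The reply does not answer the undisclosed selection in SAP 11.4, the open-label attribution without a rule for dual causes, or the lack of any endpoint for thrombo-embolism.

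**Conclusion.** The concern holds in a limited form. As written, the plan gives an AE and SAE comparison that depends on an open-label attribution and does not say so. It can mask fever, dyspnoea when recorded as worsening respiratory failure, and venous thrombo-embolism; organ failure is collected but not analysed. That is one listed reaction of ten by name and a second by plausible overlap. The overlap for dyspnoea is an assumption about how investigators would record it, since no section says so.

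The primary endpoint and the mortality comparison are not affected. The fever rates used above are assumed and serve only as illustration. The point should be fixed because the safety table cannot be read at face value without the change, but it does not undermine the trial's main analysis.

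**What to change.** - **Protocol 9.2, 9.4 and 9.5:** exempt the eight listed events from expedited reporting to the sponsor only. Record them in the CRF with onset date, seriousness and causality for every randomised participant in both arms. Reword 9.2 so that it cannot be read as dropping all non-serious AEs.
- **Protocol 9.1 and SAP 11.4:** define an AE as any untoward occurrence in a randomised participant, and give the TEAE definition a starting point that also applies to BAC patients.
- **Protocol 9.3.2:** state how to classify an event that could be due to both drug and disease.
- **SAP 11.4 and the DMC report:** tabulate the eight events by randomised arm whatever the attribution. If the CRF can no longer be changed, take the events from the medical notes and state the limitation in SAP 11.4.

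The cost is a short amendment and an eight-item CRF checklist, completed from notes already kept, for 40 patients (at most 48 in the SAP or 50 in the Protocol). No new procedures are needed. The change removes selective recording; it does not make a 30 against 10 comparison sensitive to harm.
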